Ruptured aneurysms are responsible for approximately 80-85% of non-traumatic subarachnoid hemorrhage and intracranial aneurysms (IAs) are present in 1-2% of adults in the United States⁴. An IA is a pathological dilation and thinning of a portion of the wall of an intracranial artery. While the overall risk of rupture of an IA is quite low, when rupture occurs the effect is devastating with mortality and morbidity rates that approach 50% and 30%, respectively. Aneurysmal subarachnoid hemorrhage is one of the most deadly and morbid types of strokes and represents approximately 3% of all strokes⁵. One third of these deaths occur in the first 30 days⁶. Cerebral vasospasm or delayed cerebral ischemia is a major cause of morbidity and mortality in patients who survive the initial hemorrhage. Angiographic vasospasm is evident in 30-70% of patients and can cause permanent morbidity or mortality in up to 20% of these patients⁷. Early prediction of patients at risk for development of cerebral vasospasm can help guide the aggressiveness of both medical and endovascular treatment to prevent irreversible cerebral infarction.

The mechanism behind cerebral vasospasm is not completely understood. It is suggested that there is global vasoconstriction in response to the presence of blood in the subarachnoid space. One theory is the degradation of hemoglobin results in formation of free radicals and consumption of nitric oxide. An environment with low concentrations of nitric oxide can produce both local and global vasoconstriction of the cerebral vessels⁸. The cerebral blood supply is unique in that it relies heavily on autoregulation. Under conditions of indiscriminate vasoconstriction there can be impaired cerebrovascular reactivity or ability to increase cerebral blood flow through vasodilation in response to either intrinsic or pharmacologic signals to increase CBF.

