C-arm CBCT is a technology that allows for CT images of the vasculature, bone, and soft tissues to be generated utilizing the flat detectors of modern angiography machines. This is accomplished with high speed rotation of the C-arm around a supinely positioned patient while collecting an array of 2-dimensional x-ray projections. Separately SMART-RECON algorithms are used to reconstruct the projections in anatomic planes comparable to CT images. With recent advances in technology the post-processing of images can provide both anatomic and physiologic (perfusion) information using an intravenous injection of contrast dye. This high-quality C-arm CBCT angiography utilizes 1/3 of the radiation dose currently used in our clinical practice under conventional CT imaging technology. This technique has been validated by our previously published work¹⁷⁻¹⁹.

Study Objective

The objective of this proposal is to conduct a feasibility study of acetazolamide activated C-arm CBCTP to determine its application in the prediction of symptomatic cerebral vasospasm in patients with aneurysmal subarachnoid hemorrhage. Our initial plan is to obtain C-arm CBCTP pre- and post-intravenous infusion of 1 gram acetazolamide within 24 hours of symptom onset in aneurysmal subarachnoid hemorrhage patients. Our hypothesis is that some of these patients that will later develop clinical vasospasm of a degree sufficient to cause cerebral ischemia. We believe this cohort of patients will demonstrate altered cerebrovascular reactivity during the acetazolamide challenge at a time before there is either angiographic evidence of vasospasm or clinical evidence of abnormal perfusion. Thus far in the pilot study we have enrolled a total of 10 patients and are now planning to expand enrollment to 30 patients. The data we have collected from the research scans have thus far been reproducible and collected with clinical ease. There have been no complications with imaging acquisition and there have been no safety concerns for patients. Having so far achieved our objectives with the initial 10 patients we now hope to amend the protocol to allow for the larger cohort of 30 subjects. With this larger sample size we will not only continue to assess safety and reproducibility, but also will hope to capture a large number of patients who develop vasospasm in order further assess

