All researchers and research staff involved in this project have completed Human Subjects and HIPAA training and are familiar with all procedures. The PI and co-investigators will review the data collected after the initial patients have been treated and outcome data becomes available. Adverse events or problems will be reviewed by the PI and co-investigators as they occur and will be reported to the IRB by the PI in accordance with posted guidelines. The PI and the co-investigators will meet regularly to review the data, adherence to the protocol and IRB guidelines. Data and safety monitoring will occur on a continuous basis by the research staff. The study team will meet regularly to review study progress including recruitment, data collection, and they will address any concerns or challenges that may arise. If initial pilot data shows that this technique is validated a formal study will be proposed to the IRB.

Statistical Considerations

The initial pilot study was conducted as a feasibility study and no robust statistical evaluation is possible. Since we have determined that the research imaging can be achieved safely and data reproducibly collected, we now hope to amend the cohort to a total of 30 patients so that we can capture more patients with vasospasm in order to have a more robust analysis of the correlation between percent change in CBF to Diamox and the future development of cerebral vasospasm.

IRB Concerns

The gold standard for determining if a patient has vasospasm is the clinical neurological exam. There is no currently accepted radiographic method or procedure for predicting vasospasm. Therefore, when comparing this proposed CBCT approach to the competing method we would be comparing it to the clinical neurological exam. Additionally, comparisons are being made to current methods of predicting vasospasm including TCDs, multidetector CTA/CTP, and angiography.

[figure not shown]
[figure not shown]

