With our initial 10 patients we are able to report that in all 10 patients the images were successfully required. We then performed an analysis of the 20 total cerebral hemispheres (right and left). Nineteen of 20 hemispheres demonstrated a significant change in CBF perfusion in response to Diamox ($p<0.05$). Six hemispheres demonstrated a 30% change in CBF and 12 had a 15% change. In 9 hemispheres there was the expected increase in CBF in response to Diamox. In 10 hemispheres there was a decrease in CBF. There was no statistical difference in the percent change between left and right hemispheres which would correlate with the global vasodilatory effects of Diamox. Symptomatic vasospasm then only developed in 2 of our patients. In one of these patients there was a pathological decrease in CBF in response to Diamox while the other had an appropriate increase in CBF. The goal of the analysis in this extension of the study is to better understand the changes in CBF in patients that go on to develop symptomatic or clinical vasospasm based on a change in neurological exam. Unfortunately, in our first phase of the pilot study only 2 patients developed symptomatic vasospasm. The reason we are requesting an extension to 30 patients is so we can capture a

larger number of patients with symptomatic vasospasm. Then we can assess our statistical analysis to see if we can consistently see a significant lack of response (either <30% increase in CBF or a decrease in CBF) to Diamox. With only 2 patients in our initial cohort developing symptomatic vasospasm it is impossible to make a more robust statistical proposal and that is why we are submitting a request to study more cases.

As discussed before, in this study design there is no need for a control group. We are comparing our CBCT information to the conventional method which is the clinical neurological exam change which indicates clinical or symptomatic vasospasm. The data that will be statistically compared is the pre-diamox perfusion in comparison to the post-diamox perfusion. A statistically significant change increase in CBF represents an appropriate response to Diamox. Lack of change in CBF or decrease in CBF could be suggestive of potential for developing vasospasm. More data with patients who develop clinical vasospasm is needed in order to correlate these changes with this subset of patients.

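### Thirty subjects should yield about six symptomatic vasospasm cases, too few to be called a large number or to show that cases consistently fail to respond

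*Combined protocol and SAP*

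**What the plan says.** Study Objective reports progress ("Thus far in the pilot study we have enrolled a total of 10 patients") and gives the purpose of going to 30: besides safety and reproducibility, the team "hope to capture a large number of patients who develop vasospasm in order further assess" the test as a screening tool for delayed vasospasm. Statistical Considerations is more modest: "amend the cohort to a total of 30 patients so that we can capture more patients with vasospasm". It gives no target number of cases, no precision target and no power.

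IRB Concerns gives the pilot yield: "Symptomatic vasospasm then only developed in 2 of our patients". One of the two had a fall in CBF, "while the other had an appropriate increase in CBF". The extension is then to show whether the investigators "consistently see a significant lack of response (either <30% increase in CBF or a decrease in CBF) to Diamox". The closing paragraph of that section disclaims a power analysis, treats reproducibility as settled and makes the link between CBF response and vasospasm the main aim of the expanded portion. The Data and Safety Monitoring Plan says that a formal study will be proposed if the pilot data validate the technique.

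**The concern.** Case yield is the main reason given for the extra 20 subjects, yet the documents never work out how many cases 30 subjects should produce. If the answer is a handful, the study cannot deliver what Study Objective and IRB Concerns promise.

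The plan also looks for consistency among cases only. A response pattern shared by all cases predicts nothing if it is just as common in patients who never develop vasospasm, and the pilot suggests that it is common. Because the step to a formal study depends on the technique being judged validated, a small run of concordant cases could be read as more than it is.

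**Working it through.** **Reproducing 30.** The documents give no inputs for the figure, so it cannot be reproduced. What can be checked is what it yields.

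**Inputs.** 10 enrolled, 30 in total, so 20 new (Study Objective; Study Methods). 2 symptomatic cases in 10; falls in CBF in 10 of 20 hemispheres; a 30% change in 6 of 20, direction not given (IRB Concerns).

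**Expected cases.** 20 × 0.20 = 4 new; 2 + 4 = 6 in total.

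**Range of the total.**
- True rate exactly 20%: 2 + Binomial(20, 0.2) has a 95% range of 3 to 10. The chance of 10 or more in total is 3.2%.
- The pilot rate is itself imprecise: 2/10 has an exact 95% CI of 2.5-55.6%. A beta-binomial prediction, Beta(2.5, 8.5) from a Jeffreys prior, gives a total of 2 to 13, median 6.

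**Precision of sensitivity (Clopper-Pearson).** When all n cases are test-positive, the lower 95% limit is 0.025^(1/n).

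| Result | Exact 95% CI |
|---|---|
| 6/6 | 54-100% |
| 5/6 | 36-99.6% |
| 4/6 | 22-96% |
| 10/10 | 69-100% |
| 13/13 | 75-100% |

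The last two rows are perfect results at the upper ends of the two ranges above.

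**Is 6/6 attainable?** One pilot case had an appropriate increase. If that case is test-negative, 5/6 is the ceiling with 6 cases. The documents do not settle this. IRB Concerns calls a statistically significant increase appropriate, but also counts an increase below 30% as lack of response, and that patient's percentage is not given.

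**How common is an abnormal response in non-cases?** The documents report by hemisphere, not by patient. If both hemispheres of each pilot case moved as described for the patient, non-cases account for 10 − 2 = 8 falls in 20 − 4 = 16 hemispheres, or 50%. Carrying 50% over to patients (an assumption) gives 12 abnormal of 24 non-cases.
- 6/6 against 12/24: two-sided Fisher p = 0.057. The table probabilities are 0.0313 for 6 abnormal cases, plus 0.0240 and 0.0016 for the equally or less likely tables with 1 and 0.
- 5/6 against 12/24: p = 0.20.
- Specificity of 12/24: exact 95% CI 29-71%.

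**Under the 30% definition.** If all six hemispheres with a 30% change were increases and no other reached 30%, then 14 of 20 (70%) would count as lack of response. At 70% per patient, 6/6 would arise by chance with probability 0.7^6 = 12%, with no predictive value at all.

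**The case against.** The best defence is that this is labelled a pilot feasibility study, it disclaims a power analysis, it says that two cases make a stronger statistical proposal impossible, and it defers to a later formal study. Statistical Considerations promises only more cases and a more robust analysis; 6 against 2 meets both comparatives. All of this stands, and it rules out criticising the study for lacking power or calling 30 a miscalculation. It does not cover the large number hoped for in Study Objective or the consistency sought under IRB Concerns. Those passages justify the extension after feasibility and reproducibility are declared achieved.

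A reader might go further and infer that the wrong outcome was chosen. Background and Significance says "Angiographic vasospasm is evident in 30-70% of patients and can cause permanent morbidity or mortality in up to 20% of these patients", which would be 9 to 21 of 30, while item 8 of Information Collected from Medical Records defines vasospasm by clinical deterioration or new infarct. The documents do not support that reading:
- Item 1 of the same list already collects imaging studies, and IRB Concerns uses transcranial Doppler, CTA/CTP and angiography as comparators.
- Symptomatic vasospasm is the stated target, with the neurological exam as gold standard, so the choice is deliberate.
- No follow-up vessel imaging is scheduled, so nothing shows how much vasospasm information goes unused. The 30-70% is a general rate, not one for a cohort limited to Hunt and Hess grades 2-4.
- A gain in power from the commoner outcome cannot be assumed. It would need a similar effect in milder cases and imaging in nearly everyone, and the documents establish neither.

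**Conclusion.** The concern holds as a mismatch between the stated purpose and the likely yield. About 6 symptomatic cases should be expected in 30 subjects, of which about 4 are new; a plausible total is 3 to 10 at a 20% rate, or 2 to 13 given the imprecise pilot. Even a perfect result in 6 leaves sensitivity anywhere from 54% to 100%. Agreement among cases alone would not show prediction, because falls in CBF were seen in half of the pilot hemispheres.

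The case count rests on the pilot rate carrying over to the new subjects. The Fisher results rest on an assumed 50% abnormal rate per patient in non-cases, taken from hemisphere data. The 5/6 ceiling is conditional on how the pilot case with an increase is classified. The sensitivity intervals depend only on the number of cases and positives, so the main conclusion does not need the other assumptions. The choice of symptomatic vasospasm as the outcome is not a defect.

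**What to change.** 1. In Study Objective and IRB Concerns, replace the large number and the consistency aim with the expected count: about 6 symptomatic cases in total, about 4 of them new, with the range (3-10 at a 20% rate; 2-13 allowing for pilot uncertainty).
2. State that the extension is for estimation only and cannot by itself show that the technique is validated. Align the sentence in the Data and Safety Monitoring Plan with this.
3. Report per-patient sensitivity in cases and specificity in non-cases, each with an exact 95% CI. This requires stating, before the analysis, what counts as a positive test in a patient, including how the two hemispheres are combined and whether an increase below 30% is positive. The two descriptions under IRB Concerns must be reconciled.

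The cost is a less favourable stated aim and a little more analysis; no patients, scans or follow-up visits are added. An ordered outcome using vessel imaging obtained in routine care could be added as an optional exploratory analysis, with patients who were not imaged recorded as not assessed. This point does not depend on it.

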the utility of the research study in its application as a screening diagnostic tool to predict the subsequent occurrence of delayed vasospasm in subjects with an acute aneurysmal subarachnoid hemorrhage.

Study Methods

Inclusion criteria:

A total of 30 subjects will be enrolled in this pilot feasibility study. The following patients will be targeted for enrollment:

1. Patients with aneurysmal subarachnoid hemorrhage presenting to our institution within 24 hours of symptom onset.
2. Adults, 18 years of age or older
3. Women of childbearing potential must not be pregnant (urine pregnancy test will be required as is already done as part of standard of care)

Exclusion criteria:

Whether subjects will be invited to participate in this research will be based on the patient's medical condition and will be at the discretion of the treating physician. The following patients will be excluded automatically:

1. Contraindication to acetazolamide (i.e. sulfonamide allergy, renal or liver failure)
2. Contraindication to contrast media (Allergy or abnormal serum Cr and/or GFR based on current UW guidelines for IV contrast see Appendix A)
3. Renal insufficiency, history of renal failure or renal transplant
4. Hunt and Hess grade 1 and 5 (See Appendix B, as Grade 1 have lower yield for vasospasm and Grade 5 are by definition critically ill and unstable patients)
5. Critically ill patients who are unstable and who cannot undergo scans within the proposed timeline i.e. within 24 hours of the onset of their symptoms.

Patient identification/Recruitment/Consent:

Patients targeted for enrollment will be those referred to the Department of Neurosurgery and Neuroendovascular Surgery at University of Wisconsin meeting the inclusion criteria. Eligible candidates will be identified by the neuroendovascular or neurosurgical attending physician and will be invited to participate by a clinical care team member. If patients lack capacity to provide informed consent on their own behalf, the care team will include the next of kin in the consenting process. Subarachnoid hemorrhage patients that present with a medically unstable condition will not be considered for this study.

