Overview of imaging protocol: Prior to catheter angiography, the diagnostic evaluations of subjects entered into this protocol will not vary from that used on others who are not eligible or who do not wish to participate in the study. Subjects entered into the study, will because of their participation, undergo only two additional DSA imaging acquisitions. These will be done in conjunction with their standard diagnostic DSA evaluation and consist of two CBCTPs, one before and one after administration of 1 g acetazolamide through a peripheral IV line. Each CBCTP will require administration of 75-100 mL iodinated contrast medium also through an IV line. Neither of these imaging studies will be used for clinical decision making, but would be processed and evaluated at later date for a formal analysis of the results. Following completion of diagnostic imaging subjects will receive the usual standard of care for treatment of their ruptured aneurysm i.e. endovascular embolization or open surgical clipping.

Details of experimental imaging: An initial CBCTP acquisition will be done in conjunction with injection of iodinated contrast medium through a peripheral IV (75-100 mL iopamidol, Isovue 370; Bracco Diagnostics, Princeton, NJ). An IV is placed for normal standard-of-care for this disease process. After this 1 g of acetazolamide will be given through the IV line. Following a 20-minute delay a second CBCTP acquisition will be completed again in conjunction with injection of iodinated contrast medium at a dose identical to that used for the first CBCTP acquisition. Each of the CBCTP acquisitions take less than 2 minutes so, except for the 20-minute period following administration of the acetazolamide there will be no delay in the subjects' diagnosis or treatment.

Contrast: C-arm CBCTP will be performed with intravenous injection of contrast dye (iopamidol, Isovue 370; Bracco Diagnostics, Princeton, NJ) at a rate of 4 mL/s and a maximum dose range of 75-100 mL. The contrast bolus may be followed by a 50-mL saline push at a rate of 4 mL/s. The delay will be calculated from the conventional CTA/CTP that was performed prior. The contrast administered during the conventional CTA head and neck with perfusion performed prior will be 120 mL. Therefore, the maximum amount of IV contrast media that would be administered

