within a 24-hour period for this study is 320 mL. Contrast media administration is an important consideration as a cause of iatrogenic acute kidney injury, but it should be emphasized that the large majority of these cases are minor. Under our protocol pre- and post-procedure serum creatinine levels will be monitored closely and patients will receive adequate hydration. Iopamidol is excreted mainly through the kidneys and in the absence of renal dysfunction 35-50% of the contrast media is excreted within 60 minutes and 80-90% within 8 hours. There will be at least a 1 hour period between contrast loading from the conventional CTA/CTP and the study C-arm CBCT scans.

SMART RECON: This software utilizes the images acquired during rotational angiography to create an angiographic CT. The volume set is reconstructed on the syngo MultiModality Workplace and available for assessment in less than 1 minute in the interventional suite.

Data Acquisition: Perfusion maps from the standard multi-row CTP will be evaluated with the Siemens CTP software after the procedure. Perfusion maps from the C-arm CBCT will be evaluated at an independent work station with SMART RECON. Matching regions of interest (ROI's) will be placed in each hemisphere in mirror image positions. The ROI's identified on each patient's standard CTP will be compared to ones selected in the post-processing phase.

Acetazolamide injection: 1 g intravenous acetazolamide will be administered by peripheral IV. Blood pressure, respiratory rate, heart rate and pulse oximetry will be monitored before, during, and after this injection by the administering nurse. The wait period after drug administration will be standardized to 20 minutes prior to obtaining the follow up perfusion study.

Drug Information:

Drug formulation: Solution Reconstituted, Injection

Source: Drug is on UWHC formulary and would be available through the inpatient pharmacy
Storage and stability: Store intact vials at 20-25 C (68-77 F). Store reconstituted solutions for 3 days under refrigeration at 2-8 C (36-46 F), or 12 hours at room temperature (20-25 C or 68-77 F).

Preparation: For injection reconstitute with at least 5 mL sterile water to provide solution containing not more than 100 mg/mL.

Dosage/Administration: 1 gram, intravenous

For a complete listing of drug interactions, contraindications, and adverse reactions please see:
https://online.lexi.com/lco/action/doc/retrieve/docid/uofwisconsin_f/3680280

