Acetazolamide or the brand name Diamox is an FDA-approved medication with labeled indications including glaucoma, edema, altitude sickness, and epilepsy. Our protocol will utilize intravenous formulation only. Prior studies in the literature assessing cerebrovascular reserve used rapid 1 g intravenous injection over less than 1 minute¹¹. Doses of 500 mg were reported to be insufficient for adequate carbonic anhydrase inhibition¹². Acetazolamide is

contraindicated in patients with marked renal impairment, cirrhosis or liver disease, sulfonamide allergy, adrenocortical insufficiency, or hyperchloremic acidosis.

Risks:

This feasibility study presents minimal risks to participants. Subjects entering this study will not have the timing of their therapy, whether that be endovascular or open surgery, altered in any way that would differ from the standard of care offered at our institution. The potential risks from participating in this study include contrast and radiation exposure, side effects or adverse reactions to acetazolamide and the risk of breach of confidentiality.

Contrast exposure:

The main risks are allergic reaction and contrast-induced nephropathy (CIN). Prior to receiving the additional contrast media required by our study scan subjects will have already been given a prior dose of the same contrast medium for their standard of care conventional CTA. It will thus be clear to researchers whether the subjects are able to tolerate the agent. If any patient is experiencing any sign of contrast reaction at the conclusion of the clinical CTA, they will be withdrawn from this research study.

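### Exclusion item 1 can be read as a closed list that leaves three of the protocol's own five acetazolamide contraindications not fully covered

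*Combined protocol and SAP*

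**What the plan says.** Under Study Methods, the Exclusion criteria list five grounds for automatic exclusion. Item 1 is "Contraindication to acetazolamide (i.e. sulfonamide allergy, renal or liver failure"). Item 2 is "Contraindication to contrast media (Allergy or abnormal serum Cr and/or GFR based on current UW guidelines for IV contrast see Appendix A"). Item 3 is "Renal insufficiency, history of renal failure or renal transplant". Item 4 removes Hunt and Hess grades 1 and 5. Item 5 removes unstable, critically ill patients who cannot be scanned in time.

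The closing text of Drug Information, just before Risks, gives the protocol's own statement of when the drug must not be used: it is "contraindicated in patients with marked renal impairment, cirrhosis or liver disease, sulfonamide allergy, adrenocortical insufficiency, or hyperchloremic acidosis". A little earlier the same section points to an outside drug reference, introduced by "For a complete listing of drug interactions, contraindications, and adverse reactions please see". Item 1 refers to neither.

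On the purpose of the pre- and post-acetazolamide scans, the imaging overview under Scan procedure says: "Neither of these imaging studies will be used for clinical decision making".

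**The concern.** The eligibility rule and the drug section describe the same set of patients in different terms, and the eligibility rule is the narrower. A screener working from the exclusion list, and taking the parenthesis in item 1 as the full meaning of the phrase before it, would find no automatic bar for a stable patient with adrenocortical insufficiency, hyperchloremic acidosis, or liver disease short of failure. The drug section says such a patient should not receive acetazolamide.

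What is at stake is subject safety. The drug is given solely for the study and the images do not inform care, so nothing offsets a contraindicated dose. The setting makes a complete checklist more useful: enrollment falls within 24 hours of symptom onset, the eligible Hunt and Hess grades (2 to 4) include confusion and stupor, and consent may come from next of kin. The medical history may be incomplete.

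**Working it through.** No sample-size, power or error-rate calculation applies, and the plan states no figure to reproduce. The check is a comparison of two lists plus a reading of one abbreviation.

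**Step 1. Compare the lists.** Inputs: the five comma-separated contraindications in Drug Information and the five numbered items in the Exclusion criteria.

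| Contraindication in Drug Information | Named exclusion that reaches it | Status |
|---|---|---|
| Sulfonamide allergy | Item 1 | Covered |
| Marked renal impairment | Items 1 and 3 | Covered |
| Cirrhosis or liver disease | Item 1, at the level of liver failure only | Narrowed |
| Adrenocortical insufficiency | None | Absent |
| Hyperchloremic acidosis | None | Absent |

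Covered 2 + narrowed 1 + absent 2 = 5. Not fully covered: 1 + 2 = 3 of 5. If cirrhosis and liver disease are counted separately, the result is 4 of 6; 3 of 5 follows the protocol's own grouping.

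**Step 2. Check whether the other items fill the gap.** Item 2 concerns contrast allergy and renal function. Item 4 concerns clinical grade. Item 5 concerns instability and scan timing. None mentions a liver, adrenal or acid-base condition.

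**Step 3. Check how the protocol uses i.e.** In the text available it appears three times. Besides item 1, item 5 has "within the proposed timeline i.e. within 24 hours of the onset of their symptoms" and the imaging overview has "treatment of their ruptured aneurysm i.e. endovascular embolization or open surgical clipping". Both define the term before them rather than give examples. That supports, without proving, the closed reading of item 1.

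**Step 4. Check the other safeguards.**
- The treating physician has discretion over who is invited. The text presents this separately from the automatic list.
- Medically unstable patients are not considered. This does not reach a stable patient with one of the three conditions.
- The outside drug reference is not cited in item 1. Items 2 and 4 do cite Appendices A and B, so the protocol cross-refers elsewhere when it wants a fuller source used.
- The tests the protocol itself specifies are a urine pregnancy test and serum creatinine. Neither addresses liver, adrenal or acid-base status. Other laboratory results are collected from the record, but no eligibility step uses them.

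**The case against.** The strongest reply is that the operative words of item 1 already do the job. Anyone with a contraindication to acetazolamide is excluded, and the same protocol says which conditions are contraindications. Read as a whole, the document leaves 0 of 5 open. The evidence from i.e. is thin: two other uses, neither of them a list of medical conditions, and no sign that the authors distinguish i.e. from e.g. The exclusion list is loosely drafted in any case, with renal disease in three overlapping items. Attending physicians identify the candidates, and the Study Objective section reports no safety concerns in the first 10 patients. Finally, copying unqualified liver disease into an automatic exclusion would remove patients with mild disease, and liver failure may have been a deliberate threshold.

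Much of this stands. The whole-document reading is possible, nothing shows that a contraindicated patient was enrolled, and the safeguards lower the risk. It does not remove the conflict over the liver. There item 1 addresses the organ and states a narrower threshold than the drug section, so a patient with cirrhosis but no liver failure is contraindicated in one place and outside the stated criterion in the other. If that threshold was intended, the protocol does not say so. Ten patients without a safety concern do not test the point, since nothing indicates that any of them had one of the three conditions.

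**Conclusion.** The concern holds, as a minor one. Three of the five contraindications the protocol itself names are not fully covered by any named exclusion: two are absent and one is narrowed. The count of named conditions comes directly from the text. The consequence, that a stable patient with one of these conditions meets no automatic exclusion, rests on reading the parenthesis in item 1 as a definition. That reading is reasonable but not the only one.

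The documents give no prevalence for any of the three conditions, so the number affected among the 30 subjects cannot be estimated and may be zero. No endpoint, analysis or sample-size figure is affected.

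**What to change.** Reword item 1 so that it carries the same conditions as Drug Information, for example:

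> Contraindication to acetazolamide, including: allergy to sulfonamides; marked impairment of renal function; cirrhosis or other liver disease; adrenocortical insufficiency; hyperchloremic acidosis.

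Item 3 can stay as it is, since it already covers renal insufficiency more broadly. If the sponsor did intend liver failure as the threshold, the alternative is to say so, with the reason, and to make Drug Information agree.

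Named coverage rises from 2 of 5 to 5 of 5. The cost is a one-line amendment and possibly a slightly smaller pool of eligible patients, mainly through the liver wording. The protocol is already being amended to expand from 10 to 30 subjects, so the change can go in at the same time.
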